Bupropion is an anti-depressant that increases striatal dopamine transmission,¹⁰ improves reward processing¹⁰ and is widely available at a modest cost.¹¹ The standard 300 mg/day dose of bupropion has demonstrated clear efficacy for smoking cessation in various populations.^{12,13} Outside of the smoking literature, high dose bupropion (400-450 mg/day) exhibits superior efficacy relative to the 300 mg/day dose for treating psychiatric disorders,^{14,15} reducing weight and body fat,¹⁶ and alleviating anhedonia,¹⁴ without meaningfully increasing side effects.¹⁷ Thus, high dose bupropion may be particularly effective at promoting smoking cessation in anhedonic smokers, improving anhedonia-related mental health, and preventing post-quit weight gain. To the best of our knowledge, 300 mg/day is the highest bupropion dose tested for smoking cessation in any population to date.

In this continuation proposal, we translate work in the prior period on mechanisms underlying relapse in anhedonic smokers to the development of a novel, disseminable, and putatively effective treatment for this high risk population. We propose a clinical trial in which anhedonic smokers are provided standard cessation counseling and randomized to either: the standard 300 mg/day dose of bupropion (BUP-300; N=150) or a high 450 mg/day dose (BUP-450; N=150). In addition to treatment effects on 7-day point prevalence smoking abstinence (PPA) outcomes, we will: i) examine if improvement in reward processing is a mechanism of action for BUP-450's efficacy with innovative laboratory-based computer task and subjective indices of reward processing, ii) assess moderators of treatment efficacy, iii) investigate treatment effects on secondary mental health and body weight and adiposity outcomes; and iv) utilize the extended release (XL) formulation that requires dosing only once per day, which has yet to be tested for cessation and may increase adherence.

Primary Aims

- 1. To test the efficacy of high dose bupropion for smoking cessation in anhedonic smokers.** Hyp 1. PPA rates across the 6-month post-quit follow-up period will be higher in BUP-450 vs. BUP-300.

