A recent Cochrane review found that BUP-300 mitigates the magnitude of weight gain relative to PLA and varenicline, though effects were modest and not robust at long-term follow-up.⁹⁷ Bupropion may facilitate weight loss by suppressing appetite, decreasing food reward,⁹⁸ and increasing metabolic rate via action on mesolimbic dopamine and hypothalamic melanocortin systems.⁹⁹ One of the first large trials tested the dose dependency of BUP for weight loss and showed that 400 mg/day outperformed 300 mg/day.¹⁶ Doses \geq 400mg BUP has since been the primary dose studied for weight loss, with results supporting the efficacy of BUP (vs. PLA) in various studies (2%–10% of initial body weight),^{16,17,100-103} including trials in depressed patients.¹⁰³ High dose bupropion recently garnered FDA approval for weight loss when combined with naltrexone. Because the efficacy of BUP is not dependent on a diet/behavioral weight loss intervention platform,^{16,17,100-103} **BUP-450 could prevent weight gain the smoking cessation context without weight loss counseling.** Thus, high dose bupropion may prevent post-cessation weight gain better than other cessation treatments, particularly among the population of anhedonic smokers for which weight-related health consequences are of particular concern.

A.11 Summary of the Significance of the Proposed Study

The proposed RCT of BUP-450 vs. BUP-300 aims to identify a viable method of offsetting tobacco-related health disparities facing SWPS and two other leading causes of morbidity and mortality—mental illness and excessive weight. Results will be readily translatable to real-world clinics, given the modest cost of BUP-450 and the existing prescribing practices of high dose BUP for weight loss and psychopathology. If BUP-450 does not outperform BUP-300 in quit outcomes but improves weight gain and/or mental health without additional side effects, the trial would still provide invaluable evidence of a new cessation treatment that is equally efficacious to a front line treatment (i.e., BUP-300) but has superior metabolic and/or mental health benefits.

B. INNOVATION

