Rationale for selecting BUP-300 as the sole active medication comparison. As the initial test of BUP-450 for cessation, the first question is whether BUP-450 outperforms the standard dose. Comparing BUP-450 to other front-line medications (e.g., varenicline, NRT) will be essential next steps in this line of research; yet, the sample size needed to be sufficiently powered to compare BUP-450 to BUP-300 and other active treatments is currently cost prohibitive and will be warranted pending demonstration of superiority of BUP-450 vs. BUP-300.

Why no combination pharmacotherapy? BUP-300 with varenicline may be more effective than BUP-300 alone.¹⁶⁰ BUP-300 with (vs. without) NRT comparisons are equivocal.²⁶ Testing whether in combo vs. monotherapy for BUP-450 is of interest, but would require twice the sample. One option would be to test BUP-450 vs. BUP-300 both in combination with another medication. Yet, including another treatment could washout dose effects or leave unclear whether dose differences are caused by synergism with the other treatment or stand-alone efficacy. Such a result would limit translation cases in which combo-therapy is not viable.

Type of counseling. We opted against intensive treatments, including those that address psychopathology or weight loss because they: (a) require additional counselor training, more patient burden and can be difficult to translate into clinical settings; (b) have not improved anhedonia or quit rates in anhedonic smokers (A.7);^{74,75} (c) may not be well accepted by smokers not wishing to focus on psychiatric issues or weight in a cessation counseling context; and (d) do not affect the efficacy of BUP-300 for cessation or weight loss.^{3,100} Instead, we use a brief and effective quit smoking protocol based on USDHHS practice guidelines.¹⁶¹

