Primary Aim 1: Smoking Outcome. 7-Day biochemically-verified PPA (missing coded as smoking) at 4- 8- 16- and 26-week post-quit follow-up will be evaluated using individual latent growth curve models (LGCM) for longitudinal binary outcomes including planned covariates (FTND, sex, SHAPS anhedonia score, BMI), the main effects of medication (BUP-450 vs. BUP-300), and the effect of time. Non-linear effects of time will be explored using nested likelihood ratio tests prior to evaluating hypotheses. Treatment by time interactions will be examined to characterize medication effects before and after treatment termination. To understand at what stage of the cessation process the treatments exert their effects, we will also analyze cessation milestone outcomes of attaining abstinence (yes vs. no abstinent for >24hr in the first 2 weeks post-quit), days to lapse (i.e., first puff), and days from lapse to relapse (i.e., first puff until the onset of 7 consecutive days of smoking) using logistic and cox regression. Sensitivity analyses of treatment effects will examine medication adherence and counseling visit attendance as moderator of treatment effects and we will re-analyze primary models in the subset of fully-adherent participants. Additional comparisons of side effects between the conditions will be conducted to verify tolerability of BUP-450.

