Missing data. Prior to testing primary hypotheses we will conduct exploratory analyses to determine if baseline characteristics (e.g. sociodemographics, smoking) predict patterns of missingness. Any marginally significant ($p < .10$) predictors of missingness will be included as covariates in LGCM models above and used with multiple imputation methods for evaluating obtained model estimates.¹⁹⁹ Maximum likelihood estimation of multilevel models with Mplus has the advantage of using all available data. Mplus also incorporates special facilities for maximum likelihood estimation with data missing either completely at random, or data missing at random (missing data can be a function of observed covariates) with continuous, categorical, or count outcomes and facilitates analyses using multiply imputed data.

C.8 Sample Size Considerations

We determined power/ sample size using an empirical power analysis.²⁰⁰ Estimated PPA rates for BUP-450 (45%, 38%, 30%, 30%), BUP-300 (30%, 25%, 20%, 20%) at the 4-, 8-, 16- and 26-week assessments were based on previous literature, including Cochrane Review summaries of BUP-300 effects on quitting, known

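### Section A.11 would read a failure to show that BUP-450 is superior on quitting as equal efficacy, but the plan has only a superiority test, with no margin or interval rule

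*Combined protocol and SAP*

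**What the plan says.** The fallback conclusion is in A.11, the summary of the study's significance. Its condition is: "If BUP-450 does not outperform BUP-300 in quit outcomes but improves weight gain and/or mental health without additional side effects". Its conclusion is that "the trial would still provide invaluable evidence of a new cessation treatment that is equally efficacious to a front line treatment", namely BUP-300.

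Everywhere else the plan is framed as superiority:

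- Specific Aims, Hyp 1: "PPA rates across the 6-month post-quit follow-up period will be higher in BUP-450 vs. BUP-300".
- C.3, on the choice of comparator: "the first question is whether BUP-450 outperforms the standard dose". Comparisons with other front-line medications "will be warranted pending demonstration of superiority of BUP-450 vs. BUP-300".
- C.7, Primary Aim 1: a latent growth curve model for "7-Day biochemically-verified PPA (missing coded as smoking) at 4- 8- 16- and 26-week post-quit follow-up", with medication, time and treatment-by-time effects.
- C.8: power is the share of simulated datasets with p below 0.05, under assumed abstinence of 45, 38, 30 and 30% on BUP-450 against 30, 25, 20 and 20% on BUP-300.

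The document states no equivalence or non-inferiority hypothesis and no margin. It gives no rule for reading a confidence interval and no power for a no-difference conclusion.

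**The concern.** A non-significant superiority test means that the data did not show BUP-450 to be better. That is compatible with no difference, with a real gain that was missed, and with a real loss. To move from there to equal efficacy, one needs a limit on how much worse BUP-450 could be and an interval that excludes anything beyond it. The plan has neither.

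A.11's other conditions do not fill the gap. Weight, mental health and side effects are separate outcomes, and a benefit on them carries no information about abstinence rates.

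At stake is the report of one particular result: null on quitting with a favourable secondary finding. Following A.11, the trial could be published as showing a cessation treatment equal to the standard dose when its own data still allow a material loss of abstinence. C.7 offers no other reading of a null quit result.

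**Working it through.** **Inputs.** The arm size is 150 (Specific Aims; C.4 gives 300 randomised, and C.5 gives 1:1 allocation). BUP-300 rates are 30, 25, 20 and 20%, and BUP-450 rates 45, 38, 30 and 30%, at weeks 4, 8, 16 and 26 (C.8). C.8 gives a within-person covariance range of 0.25 to 0.55 but no full matrix. I read these as correlations: 0.55, 0.40 and 0.25 at lags of one, two and three visits as the central case, and all equal to 0.25 or all equal to 0.55 as the range. Tests are two-sided at 0.05, and nothing is adjusted for the planned covariates.

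**The plan's own figures first.**

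- 300 / 0.80 = 375, which matches C.8's enrolment figure.
- Planned average gain: (15 + 13 + 10 + 10) / 4 = 12 points.
- Superiority power for the four-visit average at 150 per arm, by simulation as a stand-in for the growth model: 0.85 in the central case, 0.94 with all correlations 0.25, and 0.82 with all correlations 0.55. This is broadly consistent with C.8's figure of more than 0.83.

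**Precision if the arms are truly equal, four-visit average.** The per-person variance of the average is the sum of the 4×4 covariance matrix divided by 16.

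- Diagonal, p(1-p): 0.2100 + 0.1875 + 0.1600 + 0.1600 = 0.7175.
- Off-diagonal, central case: 2 × (0.1091 + 0.0953 + 0.0880 + 0.0733 + 0.0693 + 0.0458) = 0.9616.
- Variance: (0.7175 + 0.9616) / 16 = 0.1049.
- SE of the difference: √(2 × 0.1049 / 150) = 0.0374.
- Half-width of the 95% CI: 1.96 × 0.0374 = 0.073, or 7.3 points. It is 6.3 with all correlations 0.25 and 7.8 with all correlations 0.55.
- Relative to the planned gain: 7.3 / 12 = 61% (53 to 65%).

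**Precision at week 26.** 1.96 × √(2 × 0.20 × 0.80 / 150) = 0.0905, or 9.1 points, against a planned 10.

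**A worked result (counts are mine, for illustration).** BUP-450 has 39, 32, 24 and 24 abstinent of 150; BUP-300 has 45, 38, 30 and 30.

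- Each visit differs by -6/150 = -4.0 points, so the average difference is -4.0.
- Per-person variances are 0.0918 and 0.1052, so SE = √((0.0918 + 0.1052) / 150) = 0.0362.
- 95% CI: -4.0 ± 7.1, that is -11.1 to +3.1; z = -1.10, p = 0.27.
- Across the correlation range, the interval runs from -10.1 to +2.1 (p = 0.20) up to -11.5 to +3.5 (p = 0.30).
- If the arms were truly equal, a difference this low or lower would have probability Φ(-0.040 / 0.0374) = 0.14 (0.11 to 0.16).

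This result satisfies A.11's quitting condition, yet the interval allows a loss of about 11 points.

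**What a not-worse claim could achieve at this size.** The documents give no margin, so these are assumptions. Power = Φ(margin / SE - 1.96) with a true difference of zero.

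| Assumed margin | Four-visit average | Week 26 |
|---|---|---|
| 5 points | 24–34% | 19% |
| 7.5 points | 47–64% | 37% |
| 10 points | 71–87% | 58% |

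**The case against.** The strongest reply is about location. The sentence sits in the rationale, not among the hypotheses, endpoints or analyses, and no planned step acts on it. C.3 makes the next comparative trials depend on superiority. That stands. It keeps the severity low and confines the error to one stated conclusion. It does not make the conclusion right: this is a combined protocol and SAP, and A.11 is its only stated reading of a null quit result with secondary benefit.

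A second reply is that the figures are partly of my choosing. The worked example is an unfavourable draw, and a zero observed difference would give about ±7.3 points. Week 26 alone is not the Hyp 1 scale. The margins are assumed. All of this is fair, and the point does not depend on the example: without a margin, no interval width turns a null test into equality.

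Some stronger readings are tempting, but the documents do not support them:

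- *The trial is under-powered or its primary test is faulty.* C.8's superiority power is broadly reproduced, and the Aim 1 test is not in question.
- *150 per arm could never support a not-worse claim.* This depends on the margin. At an assumed 10 points on the four-visit average, power is 71 to 87%.
- *Coding missing as smoking would produce a known rate of false not-worse findings.* It can pull the arms together, but the documents do not fix a rate. C.8's 20% attrition is already taken off to reach 300 (375 × 0.80), the effect depends on how many of those missing do smoke, and the plan proposes no margin test.
- *Non-significant side effects will be read as equal tolerability.* C.7 says only that "Additional comparisons of side effects between the conditions will be conducted to verify tolerability of BUP-450". It does not say how a null comparison will be read, so I make no finding on it.

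**Conclusion.** A.11 is wrong as written. Failure to show superiority on quitting cannot support equal efficacy, and the weight, mental-health and side-effect conditions do not change that. At 150 per arm with equal arms, the trial would typically leave losses of up to about 7 points on the four-visit average, or about 9 points at week 26, inside the 95% interval. An observed result somewhat below zero would leave more.

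These sizes rest on C.8's control rates, on reading its covariance range as correlations, and on an unadjusted comparison; adjustment for the planned covariates may narrow the intervals somewhat. The logical point rests on none of them.

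Severity is low because this is interpretive wording. The weight and mental-health half of A.11's claim can still be tested under Aim 3.

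**What to change.** 1. **A.11:** replace the equal-efficacy wording with a statement that no difference in quitting was demonstrated, to be read with the estimate and its interval.
2. **C.7, Aim 1:** report the model-based risk difference in abstinence with its 95% CI, first for the four-visit average (which matches Hyp 1) and then for week 26. Describe a non-significant result by that interval. The risk difference can be obtained by standardising the fitted growth model's predicted probabilities, with a bootstrap or delta-method interval.
3. **Only if the sponsor wants to claim that BUP-450 is not worse:** fix and justify a margin before unblinding, and state its power. Also require the conclusion to hold under multiple imputation as well as under missing coded as smoking. C.7's missing-data paragraph already provides for predictors of missingness to be "used with multiple imputation methods for evaluating obtained model estimates".

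Items 1 and 2 cost one reworded sentence in A.11, one or two sentences in C.7 and one added estimation step. The primary test, sample size and visits do not change. The downside is that the fallback claim becomes less favourable.

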[name] et al. (2013). *Drug. Alcohol Depend.*, 133, 324-9. Anhedonia, but not other manifestations psychiatric distress, predict greater abstinence-induced deficits in acute positive affective states. In this analysis, we aimed to determine whether certain symptomatic expressions of depressive disturbance were associated with unique affective patterns of tobacco withdrawal. We found that anhedonic depressive symptoms (e.g., diminished interest, lack of pleasure) predicted larger abstinence-induced decreases in acute positive affect only (β s .17-.20). Depressive distress symptoms (e.g., sadness, worthlessness) predicted greater abstinence-induced increases in acute negative affect only (β s .24-.25). This study provided further evidence that treatments that counteract deficient positive affect during the cessation process may particularly benefit anhedonic smokers and also supported the broader transdiagnostic framework of not amalgamating symptoms by syndrome when studying the determinants of smoking among SWPS.

Output beyond testing study aims. We also leveraged the data to examine whether tobacco withdrawal or smoking reward are altered as a function of psychopathologies and other transdiagnostic vulnerabilities (e.g., hostility, anxiety sensitivity, negative urgency, PTSD symptoms, ADHD symptoms; see publication report). The study and dataset was a highly effective means of facilitating trainee career development. The data from this project produced 18 papers that first-authored by trainees, a successful dissertation, benefited post-doc who authored 6 papers and now has a tenure track position. Furthermore, [name] (Co-I), who a post-doc dur-

ing the prior funding period, author 10 papers from this project and leveraged the data to develop her own research program on sex differences in tobacco addiction in some analyses comparing men and women.^{109,110} These efforts positioned her to obtain a K01 award on ovarian hormones and other female-specific factors in tobacco addiction (K01-DA040043; PI-[name]) and a faculty position at USC. During participant recruitment, we were able to tap into a very diverse population of smokers. Owing to the large number of African-American participants we recruited who successfully completed the study protocol (N=151; 53% of sample), we were able to leverage the data to successfully compete for a new 5-year \$2M ACS grant to study the genetics of the laboratory tobacco withdrawal phenotype (RSG-13-163-01; PI-[name]) to expand of our sample to N=770 African American smokers (Current accrual N=615). Because the PI's lab has been focused on executing this fairly large study as well as another 5-year NIDA grant (R01- DA03396), there was not enough sufficient effort allocation or lab space available to move ahead with a competitive renewal for the proposed project. Hence, **the delay between the prior funding period and the proposed start date for this period was due to a lack of availability in space and effort allocation and not due to a lack of interest or productivity in the current research program**. The ACS and other NIDA R01 projects are slated to end in 2017 and 2018, making now an ideal time to pursue the proposed continuation period.

Summary. In total, the project produced 27 peer-reviewed publications, stimulated two new 5-year grants, substantively impacted trainee career development, and provided clear evidence of treatment targets for anhedonic smokers. This competitive renewal reflects a direct translation of these efforts to treatment development, which we hope will be part of a long-standing program that produces high-impact data on the nature and treatment of tobacco addiction, psychopathology, and their comorbidity.

C.2 Preliminary Studies Not Covered in the Progress Report

Anhedonia as a contributor to smoking dependence and relapse. [name] found that rates of anhedonia were higher among psychiatric outpatients with current ($n=352$) vs. past ($n=211$) nicotine dependence (59.4% vs. 47.4%, $p=.006$),³⁵ suggesting that anhedonia may contribute to difficulty quitting smoking in SWPS. In an analysis of psychopathologic dimensions as risk factors for relapse in a cessation trial (N=157), he found that pre-quit anhedonia predicted worse outcomes at 8, 16, and 26 week post-quit incrementally to somatic complaints, negative affect, interpersonal problems, nicotine dependence, cig/day, and history of MDD ($p = .002$).⁵⁶ [name] also found that among non-treatment seeking smokers (N=212), anhedonia was correlated with number of past failed quit attempts ($r=.28$, $p=.0007$) and proportion of quit attempts that ended in rapid relapse <24hr ($r=.20$) controlling for negative affect.⁸ In a lab component of the aforementioned study, anhedonic (vs. non-anhedonic) smokers were more sensitive to the effects of nicotine deprivation the urge to smoke for pleasure (Anhedonia \times Deprivation, $p=.03$), which is examined as a mediator in this trial (C.6). In the Wisconsin Smokers Health Study (WSHS) trial (N=1,504), [name] found that a single lifetime anhedonia item, which we plan to use in the proposed trial to classify anhedonic smokers, predicted greater odds of relapse at 8- and 26 weeks post quit PPA (OR=1.42, $p=.004$).⁴⁵ Even in analyses controlling for depressed mood, MDD, recurrent MDD, dysthymia, anxiety disorder, substance use disorder, nicotine dependence, and sex, quit rates were lower in anhedonic (vs. non-anhedonic) smokers. An analysis of a daily diary anhedonia measure in the WSHS showed that anhedonia at various time points pre and post-quit predicted failure to ces-

sation reach 3 cessation milestones, and relapse even amongst those given NRT.⁵⁷

Bupropion's efficacy and mechanisms of action for smoking cessation. [name] contributed to analyses of WSHS data showing that BUP-300 promotes initiation of quitting, prevents lapse, and improves 8-week PPA. [name] served as the primary methodologist in the Zyban Collaborative Trial (ZCS; N=524), which showed that BUP-300 (vs. PLA), but not CBT for depression (vs. standard) cessation counseling, improved cessation outcomes in smokers with elevated depressive symptoms (OR = 1.97, $p < .0001$).³ In collaboration with [name], he found that reductions in positive affect pre- and post-quit increased relapse risk in two trials,¹⁴³ and that urge mediated BUP-300's efficacy. In analyses of ZCS and other trials, Drs. [name] and [name] found that dopamine-related gene variants moderated BUP-300's efficacy.^{139,141}

Obesity, psychopathology, pharmacotherapy, and smoking. [name] has shown that nicotine dependence buffers the association between MDD and obesity, suggesting that depressed individuals may turn to smoking to offset the effects of MDD on obesogenic behaviors.¹⁴⁴ [name] has participated in several weight loss and obesity trials¹⁴⁵⁻¹⁴⁷ and has shown that obesity moderates the efficacy of NRT in women rendering NRT ineffective for obese female smokers.¹⁴⁸ [name] has shown that female smokers have stronger motives to smoke for mood-regulation than male smokers.¹¹⁰ [name] has done extensive research documenting the efficacy and mechanisms of naltrexone and other drugs for alcohol, smoking, and other addictive disorders in laboratory and clinical trial studies.^{127,149-154} [name] has published a series of clinical studies of the efficacy, mechanisms, and predictors of obesity treatments,¹⁵⁵⁻¹⁵⁸ including a recent paper showing that high dose bupropion's effects on weight loss are not dependent on drug-induced nausea.¹⁵⁹ In sum, Drs. [name], [name], [name], [name], and [name] have collectively produced an extensive body of work that has advanced understanding and treatment of nicotine addiction, psychopathology, weight loss, and their comorbidity and are therefore poised to successfully execute the proposed research.

C.3. Design Considerations

Rationale for selecting BUP-300 as the sole active medication comparison. As the initial test of BUP-450 for cessation, the first question is whether BUP-450 outperforms the standard dose. Comparing BUP-450 to other front-line medications (e.g., varenicline, NRT) will be essential next steps in this line of research; yet, the sample size needed to be sufficiently powered to compare BUP-450 to BUP-300 and other active treatments is currently cost prohibitive and will be warranted pending demonstration of superiority of BUP-450 vs. BUP-300.

Why no combination pharmacotherapy? BUP-300 with varenicline may be more effective than BUP-300 alone.¹⁶⁰ BUP-300 with (vs. without) NRT comparisons are equivocal.²⁶ Testing whether in combo vs. monotherapy for BUP-450 is of interest, but would require twice the sample. One option would be to test BUP-450 vs. BUP-300 both in combination with another medication. Yet, including another treatment could washout dose effects or leave unclear whether dose differences are caused by synergism with the other treatment or stand-alone efficacy. Such a result would limit translation cases in which combo-therapy is not viable.

Type of counseling. We opted against intensive treatments, including those that address psychopathology or weight loss because they: (a) require additional counselor training, more patient burden and can be difficult to translate into clinical settings; (b) have not improved anhedonia or quit rates in anhedonic smokers (A.7);^{74,75} (c) may not be well accepted by smokers not wishing to focus on psychiatric issues or weight in a cessation counseling context; and (d) do not affect the efficacy of BUP-300 for cessation or weight loss.^{3,100} Instead, we use a brief and effective quit smoking protocol based on USDHHS practice guidelines.¹⁶¹

Operational definition of "anhedonic" smokers. We will classify smokers as anhedonic based on response to a brief single anhedonia item on the Patient Health Questionnaire-2 (PHQ). The PHQ is among the most widely adopted mental health screening measures in primary care¹⁶² and is nearly identical to the SCID-5 and CIDI Anhedonia item used in psychiatric settings. Thus, classifying smokers as anhedonic and likely to benefit from BUP-450 will be highly translatable. Despite psychometric limitations of single-time measures, responses to a single-item anhedonia measures robustly differentiated cessation outcomes in our prior work.⁴⁵ A standard multi-item anhedonia scale will be included as a secondary measure (C.6). The PHQ has lifetime and current assessment frames and can use unrestricted or stringent duration thresholds (≥ 2 weeks). Though requiring anhedonia to be current and be of longer duration could exclude those with less-severe anhedonia, we opted for a more sensitive measure (i.e., any lifetime anhedonia) with a 43% prevalence rate in smokers⁴⁴ because: (1) fewer people endorse current/chronic than lifetime anhedonia, restricting generalizability to a smaller population; (2) lifetime anhedonia robustly predicts cessation outcomes,⁴⁵ (3) utilization of the any duration threshold (vs. 2+ weeks) does not affect relapse risk,⁴⁵ and (4) smokers with lifetime anhedonia who do not express

anhedonia at the time of quitting may experience anhedonia post-cessation and are therefore important to capture.⁵⁷

Why no non-anhedonic comparison? We predict BUP-450 vs. BUP-300 effects are greater in anhedonic smokers (anhedonia × treatment interaction). To test this, a comparison group of non-anhedonic smokers would be needed, which would double the N. Given this is the first RCT in anhedonic smokers and first test of BUP-450 we first establish efficacy in this high risk group and then can follow-up with larger scale multi-group trials. Instead, we examine baseline anhedonia level amongst anhedonic smokers as a moderator (Aim 2; C.7)

Why not target overweight smokers? Evidence examining pre-quit weight status as a moderator of post-cessation weight gain are equivocal, although normal and over-weight smokers both exhibit significant post-cessation weight gain.¹⁶³⁻¹⁷² Thus, targeting overweight smokers may be unnecessary and restrict generalizability. Instead, BMI will be balanced across conditions (C.5) and tested in moderator analyses (C.7).

Why begin with a pilot trial? Small pilot trials are sometimes conducted prior to full RCTs, which we plan to do for this trial. Experts conclude that such trials are useful for staff training, solidification of protocol procedures, and modification of logistical methods to maximize data collection efficiency and integrity (e.g., methods to uphold study blind).¹⁷³ As the standard clinical and scientific practices for bupropion treatment leave no substantive methodological or clinical questions, a small pilot (N=30) will be used primarily for this purpose rather than for major developmental or formative reasons. Effect size estimated based on highly stable effects of relevant prior research with BUP-300 and BUP-450 (C.8).

What about within-condition pharmacokinetic/pharmacodynamic variation in drug response? Genetic variants, biomarkers, and patient factors may introduce variance in bupropion metabolism, pharmacodynamics, and clinical outcomes,¹⁷⁴⁻¹⁷⁷ which is important in a dose-response study. It is premature to include such factors a priori in the study design, given the state of the literature. Formative laboratory research with clinical proxies (e.g., craving) could ultimately inform RCTs accounting for such factors, but would slow translation. Instead, we will bank biospecimens for possible future assays (e.g., *CYP2B6* genotype, nicotine metabolite ratio) pending funding and address patient characteristics (e.g., BMI, sex) in secondary moderator analyses.

Treatment and follow-up length. BUP-300 (vs. PLA) effects at 12 vs. 6 months do not differ²⁶ and risk of relapse due to anhedonia emerges early.^{45,56} Thus, we selected a 6-month follow-up. Differences in outcome by length of BUP-300 are modest (7 vs. 11 wk post-quit).⁸⁰ We thus chose 8-weeks post quit (+ 4-wk run-in).

C.4 Participants and Recruitment

Study site. All visits will take place at the USC Health, Emotion, & Addiction Laboratory (USC-HEAL) clinical research facility at USC Medical Center northeast of downtown Los Angeles, which is highly accessible via public transportation. USC-HEAL studies have successfully retained 1500+ daily smokers in the past 7 years. For all HEAL studies (currently there are 5), smokers are screened via a highly-efficient centralized calling center, which screens ~180 smokers per month, and places them into the appropriate study given eligibility.

Recruitment and timeline. We plan 3 months for startup, 9-months for an initial pilot, 31 months for primary trial accrual, 8 further months to complete data collection and follow-ups, and 9 months for analysis and write-up. A pilot study will be done on a subset of participants (randomize N=15 per condition) to refine procedures. The pilot will utilize the same design as the standard trial, with non-essential assessments being abbreviated for logistical purposes. Based on prior work and the efficient phone screening methods,³ we expect 16% to be ineligible at the in-person screening and 13% of consenting subjects to not complete all pre-randomization visits and be replaced. Conservatively estimating 80% eligibility and 85% randomization, 14 second-stage screens per month are needed to obtain the intent-to-treat sample of 300 randomized smokers, which had been obtained our prior 5-year trial³ using the recruitment strategies proposed here. The study will be announced via online, print, and mass media advertisements in the greater Los Angeles metropolitan area. Targeted recruitment will take place through: (1) existing research databases from USC-HEAL and [name] (Co-I; UCLA) Laboratory, which contain contact information for 2000+ daily smokers in the LA metro who wished to be called about future studies; (2) referrals from USC primary care clinics run by [name] (Co-I) and his colleagues; and (3) participants responding to advertisements to other USC-HEAL studies that are eligible for this trial.

Eligibility criteria. Inclusion: (1) Lifetime anhedonia on the PHQ-2; (2) smoking 10+ cig/day for 2+ years; (3) Aged 21-65 (21 is legal age to purchase tobacco in CA); (4) breath carbon monoxide (CO) \geq 10 ppm Exclusion: (a) past year moderate or severe DSM-IV non-tobacco substance use disorder (4+ symptoms); (b) a conservative definition of drug contraindications based on lifetime history of panic, bipolar, psychosis, bulimia nervosa, anorexia nervosa, seizure disorders, suicidal attempt (b) report of past 90-day suicidal ideation and alco-

hol withdrawal, (c) unstable cardiovascular disease (unstable angina; recent stroke/TIA < 90 days) or uncontrolled hypertension (blood pressure $\geq 150/90$), (d) severe renal/hepatic impairment based on serology evaluation (eGFR <30, AST/ALT $\geq 3 \times$ ULN), (e) current use of other cessation medications or counseling, (f) current use of e-cigarettes or other tobacco products ≥ 2 times/week, (g) recent use of bupropion containing products < 90 days, (h) current anti-psychotic, anxiolytic, antidepressant, or psychostimulant medication; (g) currently or plan to be pregnant (based on urine HCG) or active breastfeeding.

Sex/ethnicity. We expect our sample will parallel the diversity of Los Angeles County, as in samples collected in our prior research (3% Asian, 53% Non-Hispanic Black, 37% White, 7% other, 13% Non-Black Hispanic),⁹ and balanced on sex. Targeted recruitment will be applied to ensure adequate representation of each group.

Retention. Retention procedures involve: (1) escalating incentives for follow-ups (\$25, \$50, \$75, \$150); (2) incentives for baseline assessment and completing supplemental measures for mediator hypotheses (\$25 per visit); (3) obtaining social networking user contact info, emails, phone numbers of close friends/relatives to track participants not reachable via personal cellphone; (4) keeping participant burden as low by limiting visits and measures to what is scientifically and medically necessary; and (5) permitting phone counseling when possible. Using similar procedures in previous trials we have been involved in, 81.3% of subjects completed all follow-ups and 2.3% were entirely lost to follow-up in a 12-month BUP-300 trial.³ In a fluoxetine trial we took part in with an extended 8-week pre-treatment run-in, only 6.5% were lost to follow-up.²¹

C.5 Procedure

Screening. After phone screen, an in-person screening will include both written and verbal informed consent, psychiatric interview, breath CO, urine pregnancy test, blood collection for labs, baseline assessments (C.6), and medical screening involving a physical exam. At the start of the baseline visit, the project team will explain the study and obtain written consent to participate. The study physician will review the medication with participants and obtain additional verbal consent to participate after reviewing the study treatment. Those ineligible will be provided referral information for psychiatric, addiction, family planning/OB (if appropriate) and smoking cessation (California quit line) resources. For participants who report past 30-day suicidal ideation, a suicide assessment screening protocol will involve a systematic assessment for emergent events, as well as referral to emergency mental health treatment and referral to a suicide prevention crisis hotline. In cases in which participants endorse current suicidality on the SCID-NP, [name] (or an available commensurately trained clinician if [name] is unavailable) will be called and will conduct a suicide risk assessment and protocol with the participant. If the participant appears at high risk and/or cannot contract for safety, emergency services will be called. To further monitor risk for suicide and/or self harm, study staff will review all questionnaire items that enquire about the presence of suicidal thoughts or ideations.

Randomization. Eligible participants will be randomized in a 1:1 ratio using urn randomization¹⁷⁸ for balance on sex, level of nicotine dependence (Fagerström Test for Nicotine Dependence; FTND),¹⁷⁹ BMI, and current anhedonia level (Snaith Hamilton Pleasure Capacity Scale; SHAPS)¹⁸⁰ across conditions.

Schedule. Participants will attend a pre-treatment visit involving eligibility screen and baseline measures (1-2 visits depending on physician availability), 7 in-treatment, and 3 post-treatment follow-up visits (C.6). On some visits subjects will complete supplemental measures of mediators (C.6). Certain visits will occur via phone if preferred by participant (Table).

Week	Pre-R**	-4	-2	-1	0	1	2	4	5-7	8	16	26
		Pre-quit Tx			Post-quit Tx					Post-tx F/U		
Counseling		X	X	X*	X	X*	X*	X				
Medical visit/labs	X***	X								X***		
Medication		X	X	X	X	X	X	X			X	
Core Ax		X	X	X	X	X	X	X				
Supplemental Ax		X	X		X			X				
Outcome Ax	X						X			X	X	X

